2.3 Potential Risks and Benefits

Potential risks in this study could relate to the interventions to be implemented and to data security. The control group will receive usual standard of care. The intervention group will receive interventions that are already accepted as best practices. None of the proposed interventions are experimental. The study team will capture important safety data as part of the study outcomes: hospitalizations, 30-day readmissions, ER visits, cardiovascular events and death. In addition to outcome data and to maximize patient safety the study team will capture, review monthly and report quarterly to the DSMB data on the following events in the intervention group: hypotension, syncope, hyperkalemia, electrolyte disturbances, angioedema, hypoglycemia, rhabdomyolysis, myositis, drug toxicity, pregnancy while treated with ACEI or ARB, acute kidney injury, reductions in eGFR 50% or higher initiation of dialysis.

There are inherent risks associated with use of patient data the study and careful attention has been put in place to maximize data safety and protect patient privacy and confidentiality. Transmission of identifiable patient data will occur through secure FTP of HL7. Patient data will be stored in a secure database on the FISMA compliant VAZATA cloud. Access to the database will be password protected. Communication and files will be encrypted. Patient data will be de-identified prior to submitting for analysis. The approach has been already used safely at 2 of the participating healthcare systems. At this time it is anticipated that the VA North Texas Health Care System will carry out study implementation within their firewall and that patient identified data from the VA will not be transferred to the cloud at least in early stages of the study.

There are several important benefits that may result from this study. Implementation of best care practices for patients with CKD, diabetes and hypertension may improve very important clinical outcomes. Furthermore, successful implementation of this model can lead to more effective strategies to care for patients with other multiple chronic medical conditions and improve strategies for population health management. Finally, the research infrastructure developed for this study can be a model for future pragmatic trials.

3. Objectives

The overall goal of the study Improving Chronic Disease Management with Pieces (ICD-Pieces) is to improve the care of patients who have the triad of chronic kidney disease, diabetes, and hypertension. The general hypothesis is that patients who receive care with a collaborative model of primary care-subspecialty care interventions enhanced by novel information technology and practice facilitators will have fewer disease-specific hospitalizations, readmissions, all-cause hospitalizations, cardiovascular events and deaths than patients receiving standard medical care.

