7.3 Follow up Visits

Measures of blood pressure, blood glucose, kidney function (creatinine, eGFR), lipid levels, urine protein/urine albumin as well as pre-specified safety events will be captured from electronic health records at the time of patient contacts with the healthcare system for scheduled or unexpected visits for patients. Information will be then directed to primary care teams per study protocol.

Main study outcomes will be captured throughout the study for both intervention and control groups using the same tools in the electronic health record and access to DFW Regional Hospital Council, ProHealth database and VA electronic information systems.

The study does not specify the frequency of visits for study participants. It is anticipated that patients with the triad of CKD, diabetes and hypertension will usually be seen at a minimum of every 3-6months in most participating clinics.

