9.1 Specification of Safety Parameters

Adverse safety events will be captured and monitored as part of the study. The primary outcome of this trial is all-cause hospitalizations for patients with a triad of CKD, diabetes and hypertension and all unplanned hospitalizations will be captured. The main secondary outcomes that will be captured in the study also include safety events including 30-day all cause readmissions (for those patients who have an index hospitalization), emergency room visits, cardiovascular events, deaths, and disease-specific hospitalizations. In this study disease-specific hospitalizations include all those hospitalizations for cardiovascular complications, congestive heart failure, volume overload, hypertension complications, acute coronary syndrome, myocardial infarction, coronary/peripheral revascularization, stroke, amputation/limb ischemia, uncontrolled diabetes, hypoglycemia, diabetes complications, acute kidney injury, hyperkalemia, electrolyte disturbances, medication errors, drug toxicity, and infections.

In this study the control group will receive standard of care. The intervention group will receive interventions that are already accepted as best practices. Primary care providers will make ultimate decisions regarding implementation of any of the interventions for both groups. In addition to the study outcome measures detailed above the following events will be captured and reported (whether they lead to hospitalizations or not) as they could be related to potential study interventions: hypotension, syncope, hyperkalemia, electrolyte disturbances, angioedema, hypoglycemia, rhabdomyolysis, myositis, drug toxicity, pregnancy while treated with ACEI or ARB, acute kidney injury, reductions in eGFR 50% or higher, or initiation of dialysis.

The study will monitor for any malfunctions on the decision support software system and SFTP used for data transmission to and from electronic health records of the study sites for Parkland, THR, ProHealth and VA of North Texas. There will also be monitoring for adherence to Manual of Procedure interventions including identification and enrollment of eligible patients, activation of study protocols and recommended follow up.

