9.2 Methods and Timing for Assessing, Recording and Analyzing Safety Parameters

9.2.1 Adverse Events

The study outcomes and adverse/safety events detailed in Section 9.1 will be captured directly from the electronic health records of the participating healthcare systems, DFW Hospital Council and internal databases and event tracking forms from ProHealth and VA of North Texas as previously described. In this pragmatic trial capture of unsolicited events can occur in most instances from the electronic health records and databases. As noted above there will be confirmation for solicited adverse event including hospitalizations for patients from the VA of North Texas who may be seen in other institutions in Dallas/Fort Worth.

Adverse events will be collected throughout the entire participation of subjects in the study (12 months from enrollment to completion of the study participations for each subject). The study coordinating team will review adverse events to determine relatedness to study interventions and to grade severity as needed.

Adverse events will be classified as severe or mild/moderate. For the purposes of this study severe adverse events will include those leading to death, hospitalizations, or permanent disability/incapacity. Other safety events will be classified as mild/moderate. As the study relies heavily on event capture via the electronic health records it may not be possible in all instances to accurately differentiate between mild and/or moderate severity within the context of this pragmatic trial.

The study team will make determinations on whether serious adverse events are possibly/likely related to study interventions.

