9.2.4 Unanticipated Problems

The study team will remain vigilant for unanticipated problems. Trends of increasing frequency or rate of safety events in the intervention group will prompt review of individual cases by the study team and reporting to the oversight group (DSMB).

Other possible unanticipated problems including malfunctioning of the decision support system or non-adherence to recommended clinic protocols as well as possible mitigations are discussed in Section 13 Quality Control and Quality Assurance.

9.2.5 Procedures to be Followed in the Event of Abnormal Laboratory Test Values or Abnormal Clinical Findings

All participating subjects in the study including in both control group and intervention group will be under the direct care of primary care providers who will make final decisions on all interventions and direct patient care. Abnormal laboratory findings or clinical findings will be brought to the attention of the primary care provider according to the existing protocols in each healthcare system for appropriate clinical response.

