9.3 Reporting Procedures

The study group will collect adverse events from all the participating healthcare systems and review at least monthly. There will be reports prepared for submission to the DSMB quarterly.

It should be noted that there will be some delay on the acquisition of data regarding some adverse events/outcomes. Hospitalizations which are not captured via the electronic health record but require reporting from the DFW Hospital Council may not be known by the study team for several months. Furthermore, information on other serious adverse events such as deaths may not be available to the study team until after review of the Social Security Death files.

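### Section 2.3 confines the additional safety events to the intervention group, sections 9.1, 9.2.1 and 9.3 do not, and nothing promises the DSMB these events by arm

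*Combined protocol and SAP*

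**What the plan says.** Section 2.3, after naming the trial outcomes as safety data, adds a further list and says that "the study team will capture, review monthly and report quarterly to the DSMB data on the following events in the intervention group". The list has 13 items: hypotension, syncope, hyperkalemia, electrolyte disturbances, angioedema, hypoglycemia, rhabdomyolysis, myositis, drug toxicity, pregnancy on an ACEI or ARB, acute kidney injury (AKI), an eGFR fall of 50% or more, and starting dialysis.

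Section 9.1 gives the same 13 items, shortly after describing the care of both groups, and says that "the following events will be captured and reported (whether they lead to hospitalizations or not) as they could be related to potential study interventions". It names no arm. Section 9.2.1 continues in the same way: "The study outcomes and adverse/safety events detailed in Section 9.1 will be captured directly from the electronic health records of the participating healthcare systems", and "Adverse events will be collected throughout the entire participation of subjects in the study". Section 9.3 has adverse events from all participating systems reviewed at least monthly, and then: "There will be reports prepared for submission to the DSMB quarterly". Neither section limits this to one arm, and neither says that the reports are split by arm.

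Section 7.3 says that laboratory and blood pressure measures "as well as pre-specified safety events will be captured from electronic health records at the time of patient contacts with the healthcare system", again without an arm. Its explicit statement that both groups are captured with the same tools is confined to the main study outcomes.

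Section 9.2.4 makes a rising frequency or rate of safety events in the intervention group the prompt for case review and a report to the DSMB. It mentions no comparison with control.

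**The concern.** The two descriptions lead to different work. A team that follows section 2.3 would run the event queries on intervention records and send the DSMB a one-arm table. A team that follows sections 9.1, 9.2.1 and 9.3 could query everyone.

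The DSMB can halt the trial on patient safety grounds (sections 5.4, 9.5 and 9.6). These patients have CKD, diabetes and hypertension, so low blood pressure, high potassium, hypoglycemia and kidney injury will occur under usual care as well. With counts from one arm only, the DSMB could miss a real excess, or could react to ordinary background.

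A second difficulty concerns the laboratory-detected events. Where a practice activates the Appendix I protocols, creatinine and potassium are checked after each start or increase of an ACEi or ARB, and again at diuretic follow-up. More testing finds more abnormal values. Without a control count, and without the number of tests behind each count, better detection can look like harm.

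**Working it through.** No figure in the plan is at issue and there is no arithmetic to reproduce. The check is a comparison of every place that governs capture, review or DSMB reporting of safety events.

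| Section | What it governs | Arm stated |
|---|---|---|
| 2.3 | Capture, monthly review and quarterly DSMB report of the 13 events | Intervention only |
| 9.1 | Capture and reporting of the same 13 events | None |
| 9.2.1 | Source and period of adverse event collection | None |
| 9.2.2 | Manual review: first 100 subjects per healthcare site, then at least 10 per system each quarter | None |
| 9.2.4 | Trigger for case review and DSMB report | Intervention only, no comparator |
| 9.3 | Monthly review, quarterly DSMB report | None, and no split by arm |
| 9.4 | Monitoring by Pieces and facilitators | Intervention only |
| 7.3, pre-specified safety events | Capture at patient contacts | None |
| 7.3, main outcomes | Capture with the same tools | Both |
| 6.7 | Comparison of utilization rates | Both, DSMB not named |
| 4, interim analysis | Efficacy at 50% of primary outcome data | Comparative by nature, listed events not covered |
| 4, quarterly trend review | Concerns passed to the DSMB | None, no by-arm tables |

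Three things follow.

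1. Section 2.3 states a one-arm rule for capture and reporting. Sections 9.1, 9.2.1 and 9.3 state a rule with no such limit. Within section 9, only 9.2.4 and 9.4 name the intervention group: the first sets a trigger and the second describes ongoing monitoring. Neither limits capture or the routine quarterly report.
2. No row commits to giving the DSMB the listed events by arm.
3. The gap differs by event. Secondary objective (d) in the Protocol Summary covers AKI, eGFR change, electrolyte disturbances and drug toxicity even without admission. Sections 3.1.2.4, 3.2.2 and 4 make safety events, AKI and eGFR change objectives or secondary outcomes, with no arm limit. For AKI, eGFR change and electrolyte disturbances, control data are therefore probably captured, and what is missing is the commitment to show them to the DSMB by arm. Hypotension, syncope, angioedema, myositis and rhabdomyolysis are not named among the objectives or outcomes. Only the general reference to safety or adverse events could reach them, so for these five section 2.3 may also decide whether control data are captured at all.

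On testing, the ACEi/ARB protocol in Appendix I schedules a creatinine and potassium check 1 to 3 weeks after each start or increase, and the diuretic protocol orders both tests before each 2 to 4 week follow-up. Section 6.5 makes activation optional. The direction of the detection effect is clear. Its size cannot be derived, because the documents state neither how often the protocols will be activated nor how often control patients are tested.

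**The case against.** The strongest reply is that this is silence set against a specification, and not a contradiction. Section 9.1 lists the events because they may be related to the interventions, and sections 9.2.1 and 9.2.2 centre review on relatedness. On that reading, section 2.3 describes an extra layer of vigilance where new exposure arises and was never meant to switch off capture in controls. A DSMB charter or report template could also specify by-arm tables; none is among the documents, so its content can be neither assumed nor ruled out.

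Part of this stands. The extra-layer reading is possible, and it is why the point does not go further than it does. But section 2.3 uses the word capture as well as review and report, and no other section restores the control arm for these events. Relatedness review of single cases also does not replace a concurrent rate when the events are common in the background.

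Two stronger readings are tempting. A reader might infer that no control-arm safety data will be collected. The documents do not support that: both-arm capture of the main outcomes is explicit, and AKI, eGFR change and safety events are secondary outcomes without an arm limit. A reader might also set the Appendix I checks against the remark in section 7.3 that patients "will usually be seen at a minimum of every 3-6months in most participating clinics" and derive a testing ratio between the arms. That would assume one creatinine and potassium test per routine visit, which the plan does not state. It would also have to account for baseline checks, repeat potassium tests and pre-diuretic laboratory work, and for patients already on treatment at entry. No ratio is offered for that reason.

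**Conclusion.** The inconsistency is real and should be resolved. Under section 2.3 as written, the DSMB would have no concurrent control rate for listed events that do not lead to an admission, emergency visit or death, and the trigger in section 9.2.4 would have nothing to compare with. Admissions, emergency visits, cardiovascular events and deaths are outside the capture gap, because they are outcomes in both arms. The plan does not explicitly promise by-arm DSMB tables for those either, but the control data will exist.

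The size is qualitative. All 13 listed events lack a stated by-arm route to the DSMB, and five of them may lack control-arm capture as well. The documents give no rates for these events, so no number of missed or falsely flagged events can be given.

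The conclusion rests on two assumptions: that section 2.3 would be applied as worded, and that no charter outside these documents already requires by-arm safety tables. If the second is wrong, what remains is a wording correction. Confidence is medium.

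**What to change.** Reconcile sections 2.3 and 9.2.4 with 9.1, 9.2.1 and 9.3:

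- State that the listed events are captured in both groups with the same record queries, and reported to the DSMB quarterly by arm with denominators.
- For laboratory-detected events (AKI, hyperkalemia and other electrolyte disturbances, eGFR falls), show the number of tests per patient by arm next to the event counts.
- Let the case review in section 9.2.4 also be prompted by an excess over control, and keep the existing trigger.

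Formal cluster-adjusted differences each quarter are optional; counts and denominators by arm are enough to close the gap. Section 9.4 and the extent of manual chart review can stay as they are.

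The cost is modest. Section 6.2 already has Pieces accessing the records of all patients at participating sites, so the control queries need no new visits or data collection. The downside is analyst time, longer quarterly DSMB reports, and queries run locally at the VA, whose patient data stay behind its firewall at least early in the trial (sections 2.3 and 6.2).

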3.1 Study Objectives

3.1.1 Primary Objective

The primary objective of the study is to test the hypothesis that a collaborative model of primary care enhanced by novel information technology and practice facilitators to leverage data from electronic health records will allow accurate identification of patients with the triad of CKD, diabetes and hypertension using objective and reproducible criteria, and provide clinician support for implementation of best practices of care, monitoring clinical measures, adjusting treatments and reduce 12-month hospitalization rates. In this study disease-specific hospitalizations for CKD, diabetes and hypertension include hospitalizations due to cardiovascular complications, congestive heart failure, volume overload, accelerated/malignant/uncontrolled hypertension, acute coronary syndromes, myocardial infarction, stroke, coronary/peripheral revascularization, limb ischemia/amputations, diabetes complications, uncontrolled diabetes, hypoglycemia, acute kidney injury, hyperkalemia, electrolyte disturbances, medication errors, drug toxicity, and infections.

3.1.2 Secondary Objectives

3.1.2.1

The study will test if implementation of the collaborative model of primary care-subspecialty care interventions will reduce 30-day readmissions (for patients who are hospitalized), emergency room visits, cardiovascular events, deaths or disease-specific hospitalizations. In this study disease-specific hospitalizations for CKD, diabetes and hypertension include hospitalizations due to cardiovascular complications, congestive heart failure, volume overload, accelerated/malignant/uncontrolled hypertension, acute coronary syndromes, myocardial infarction, stroke, coronary/peripheral revascularization, limb ischemia/amputations, diabetes complications, uncontrolled diabetes, hypoglycemia, acute kidney injury, hyperkalemia, electrolyte disturbances, medication errors, drug toxicity, and infections.

3.1.2.2

Develop and validate predictive models for risks of hospitalizations, emergency room visits, cardiovascular events and deaths for all patients with coexistent CKD, diabetes and hypertension and predict risks of 30-day disease-specific readmissions for patients who are hospitalized.

3.1.2.3

Capture data (demographic, clinical, medications, laboratories, procedures) to phenotype patients with a triad of CKD, diabetes and hypertension.

3.1.2.4

Obtain important safety data for patients with CKD, diabetes and hypertension including adverse safety events, acute kidney injury and progression of chronic kidney disease (even for patients not hospitalized).

3.1.2.5

Obtain information on resource utilization including not only hospitalizations but also all emergency room visits, outpatient visits and diagnostic and therapeutic procedures.

3.1.2.6

Patient Reported Outcomes (PROs) are increasingly recognized as key outcomes of clinical studies challenges of obtaining direct consent from study patients and obtaining data from the control group prevent us from complete capture of PRO at this stage. We do plan to submit a proposal to capture PROs for both intervention and control groups at completion of the study. The objective will be to evaluate the impact of the collaborative model of care on patient related outcomes (PROs) including health-related quality of life, patient satisfaction, patient perspective on quality of their care and measures of patient perception of burden related to care of their CKD, diabetes and hypertension.

3.1.2.7

Evaluate the impact of the collaborative primary care-subspecialty care model on provider satisfaction with resources and ability to manage patients with coexistent CKD, diabetes and hypertension.

3.2 Study Outcome Measures

3.2.1 Primary Outcome Measures

The primary outcome of this trial is all cause hospitalizations for patients with a triad of CKD, diabetes and hypertension. Specifically, the outcome will be hospitalization rates at 12 months for study participants. We will include both regular hospitalizations as defined by CMS and observation status overnight (to avoid variations related to definition of inpatient status/hospitalization using the recent implementation of the “two midnight rule” CMS-1599-F).

Hospitalizations can be ascertained objectively from the electronic healthcare record with assistance of electronic tools in each of the participating healthcare systems. If there is difficulty with adjudication of hospitalization, the steering committee will review and make a final recommendation. It is possible that some patients may be seen at a healthcare system other than one of the participating sites in this study. To maximize completeness of outcome data acquisition we will also track study patients with data from the Dallas Fort Worth Hospital Council that is a cooperative regional-sharing initiative that allows matching patients with any hospitalizations in any hospital in Dallas-Fort Worth. Patients in ProHealth in Connecticut are part of an Accountable Care Organization that receives regular and detailed reports from all hospitalizations for their members. Patients followed at the VA of North Texas may have hospitalizations outside the VA System and not tracked by the DFW Hospital Council. We will address this challenge in several ways. First, VA internal databases capture if payments have been initiated for outside hospitalizations. Second, we plan to include a standard question to the clinic workflow to ask patients about recent hospitalizations. Third, we have initiated discussions about the possibility of tracking hospitalizations of patients from the VA of North Texas via the DFW Hospital Council.

